#### Abstract

This document defines the Clinical Investigation Protocol for a study designed to determine whether blood loss after spontaneous vaginal delivery is altered by the addition of misoprostol administration to the standard use of intravenous oxytocin after delivery. The protocol is an open-label randomized prospective trial to be carried out at Queens Hospital Center.

Blood loss will be measured indirectly by comparing the maternal hemoglobin and hematocrit levels on admission in labor to those obtained within 24 hours after delivery.

## Background

Some maternal blood loss normally occurs at the time of vaginal delivery. The best estimates indicate that a loss of approximately 500 mL is average, with a range of about 250-700 mL.[1,2] Some of this bleeding arises from birth canal lacerations or surgical incisions (i.e., episiotomy), but most derives from the vessels exposed in the uterine wall at the placental site once the placenta has separated.

Under normal circumstances, shortly after placental separation intense myometrial contractions occur. These raise the pressure within the myometrial wall above that of the blood pressure in the vessels that traverse it, vessels that opened into the intervillous space. Flow in these vessels is thus mechanically attenuated by myometrial contraction, allowing for the formation of intravascular thrombi.

This mechanism for controlling postpartum uterine blood loss works well most of the time. If, however, the uterus remains hypotonic or atonic after delivery, excessive blood loss can occur. In the worst cases, severe uterine hemorrhage ensues. Postpartum hemorrhage is, in fact, the leading cause of maternal mortality in the world, accounting for at least 100,000 deaths annually.[3] Even in the absence of frank hemorrhage, postpartum blood loss can result in maternal anemia. Recuperation of iron stores to recover from this blood loss takes time, and may not occur, especially in low socioeconomic areas where dietary iron consumption is often deficient, and pregnancies tend to occur in close succession.

Postpartum anemia is a significant contributor to short- and long-term morbidity.[5-7] It increases the risk of infection and poor wound healing. Also, the associated fatigue may interfere with the mother's ability to administer child care and to bond appropriately with her infant. Anemic mothers tend to have more difficulty with nursing, and may produce iron-deficient milk. There is thus a strong rationale to minimize postpartum blood loss.

In most US hospitals, parturients receive a high dose of intravenous or intramuscular oxytocin immediately after delivery. This approach has been shown in several studies to reduce the risk of postpartum hemorrhage, [8-11] and is practiced routinely at Queens Hospital Center. We employ an intravenous infusion of oxytocin (Pitocin®) at a rate of about 50-100 mU/minute. Despite this approach, there is still substantial blood loss at delivery, based on our preliminary observations shown below. This provides the rationale to determine whether use of an adjunctive drug, namely misoprostol 600 µg rectally, administered after delivery, might reduce blood loss further than does oxytocin alone, thus decreasing the risk of morbidity related to postpartum anemia.

## **Preliminary Data**

We examined the hemograms of a randomly chosen consecutive sample of 53 spontaneous vaginal deliveries performed at Queens Hospital Center between September 15 and October 1, 2010.

Among these patients, the admission hemoglobin concentration was 11.9±1.2 g/dL and that on the first postparutum day was 10.9±1.3. The mean fall was 1.02 (95% CI 0.74, 1.29), a statistically significant decrease (P<0.0001). Hematocrit levels fell in parallel, by an average of 7.8% of the predelivery value. The mean fall in hemoglobin and hematocrit levels after delivery (1.02 g/dL and 2.81%) is consistent with an average blood loss of about 500 mL. The consistency of these changes and the small associated variance indicate that the change in hemoglobin and hematocrit levels is a meaningful proxy for the assessment of blood lost during vaginal delivery.

## Study Design

The study is a prospective randomized open-label clinical trial to be performed in a single institution. It will compare the intrapartum and postpartum maternal blood hemoglobin concentrations and hematocrit measurements in a group of parturients who received standard prophylactic intravenous oxytocin immediately after delivery with a group that received oxytocin and adjuvant misoprostol.

#### Sample size and analysis

A total of 800 subjects will enter this two-treatment parallel design study. With that sample size, the probability is 90% that the study will detect a treatment difference at a two-sided 0.05 significance level if the difference in hemoglobin concentration between treatments is 0.3 g/dL. This analysis is based on the assumption that the standard deviation of the postpartum and intrapartum hemoglobin concentrations is not larger than 1.3 g/dL.

Comparison of intrapartum and postpartum hemoglobin and hematocrit levels will be done using a paired t-test. A probability level of 0.05 will be used as the threshold for significance.

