#### Inclusion and exclusion criteria

This study will include adult pregnant women regardless of age. Pregnant minors under the age of 18 will not be eligible.

A patient will be considered for inclusion in the study if she meets all of the following criteria:

- She has a term (≥37 completed weeks) live singleton gestation in cephalic presentation and has been admitted to the Labor and Delivery Unit
- She is in the latent phase of labor or has been admitted for induction of labor or at prenatal clinic visit
- She has had fewer than four prior vaginal deliveries.
- She reports no allergy to misoprostol.

The following factors or conditions will exclude a patient from consideration as a subject:

- The fetus has a known major fetal malformation or chromosome abnormality
- The gestation is multiple.
- There is a breech or other malpresentation
- The patient reports involvement in another clinical trial currently or previously in this pregnancy.
- The patient is expected to have a cesarean delivery.
- The patient had a prior cesarean delivery.
- There has been an intrauterine fetal death.
- There is polyhydramnios (amniotic fluid index >22 cm).
- Presence of acute or chronic renal disease
- Presence of preeclampsia

Of subjects who enter the study, the development of certain conditions will exclude them post hoc from receiving misoprostol under the protocol, and from the data analysis. These conditions include:

- Unanticipated cesarean delivery.
- Performance of episiotomy (third and fourth degree extensions will be excluded).
- Vaginal or cervical laceration, or perineal laceration of more than second degree in depth.
- Severe postpartum hemorrhage requiring intervention immediately after delivery.
- Uterine rupture
- Placental abruption.
- Patient withdrawal of consent.

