# Study Procedure

Informed consent will be obtained by one of the investigators or informed consent delegates. The subject will then be assigned randomly to the control (oxytocin alone) or the study (oxytocin + misoprostol) group, as described above. The subject and her medical caretakers will be informed of which group she is in. If the labor eventuates in a vaginal delivery, all subjects will receive the standard dose of intravenous oxytocin, begun within one minute of delivery. Subjects in the study group who have not incurred any of the post-hoc exclusion criteria (episiotomy, major laceration, etc) will receive a dose of 600 µg of misoprostol in addition to their oxytocin. This will be administered in the form of six 100 µg tablets inserted approximately 2 cm into the anorectal canal by the obstetrician or midwife who has performed the delivery. The common method for administering Misoprostol for postpartum hemorrhaging is rectally for local absorption. Since this study is directed toward prevention instead of treatment, the dosage of 600mg is a lower dosage from the 1000mg administered, as standard practices, for treating postpartum hemorrhaging of more than 500cc estimated blood loss. patient's vital signs will be recorded after delivery according to standard protocols of the obstetric service. The Data Collection forms will be filled out after the delivery by one of the investigators. The measurement of postpartum hemoglobin and hematocrit (H & H) is automatically ordered at 06:00am for all patients who have delivered the day prior, constituting this measurement at "Postpartum Day 1", which is at a minimum of 6 hours after delivery and is enough time for H & H levels to stabilize.

Within 36 hours of delivery, additional information will be collected from the patient's record, including the postpartum hemogram and information about any symptoms or signs related to the misoprostol.

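### The plan powers a between-arm difference but names only a paired before-and-after t-test, and its 90% power belongs to the 800 women entering, not to the number analysed

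*Combined protocol and SAP*

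**What the plan says.** All references are to the combined protocol and SAP.

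- **Question.** Study Design sets women given oxytocin alone against women given both drugs: it compares the first group "with a group that received oxytocin and adjuvant misoprostol".
- **Power.** Sample size and analysis has 800 women entering two parallel arms and says: "With that sample size, the probability is 90% that the study will detect a treatment difference at a two-sided 0.05 significance level". The difference is 0.3 g/dL between treatments. The assumption is that "the standard deviation of the postpartum and intrapartum hemoglobin concentrations is not larger than 1.3 g/dL".
- **Test.** The same section continues: "Comparison of intrapartum and postpartum hemoglobin and hematocrit levels will be done using a paired t-test". No other test is named anywhere.
- **Order of events.** Under Study Procedure, randomization follows consent and precedes delivery: "The subject will then be assigned randomly to the control (oxytocin alone) or the study (oxytocin + misoprostol) group".
- **Exclusions after entry.** Inclusion and exclusion criteria lists seven conditions arising after entry that "will exclude them post hoc from receiving misoprostol under the protocol, and from the data analysis". No expected rate, inflation or analysed number is given.
- **Episiotomy.** That list has "Performance of episiotomy (third and fourth degree extensions will be excluded" (the parenthesis closes there). Study Procedure refers to women "who have not incurred any of the post-hoc exclusion criteria (episiotomy, major laceration, etc" and puts no limit on episiotomy.

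**The concern.** The stated power and the stated analysis concern different hypotheses. The 90% is the chance of showing that two arms differ by 0.3 g/dL. The paired t-test asks whether a woman's hemoglobin is lower after delivery than before, which the site's pilot has already answered. Followed literally, the plan yields no test of misoprostol. If a between-arm test is intended, the choice among postpartum level, change from admission and adjusted level stays open until after the data are seen, in an open-label trial.

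Two further gaps separate the 90% from the analysis. It is computed on women entering, although some will be removed. It also uses a ceiling on the SD of hemoglobin concentrations, whereas the Abstract and Preliminary Data treat the change from admission as the measure of blood loss. The first gap lowers power and the second probably raises it, so the printed figure describes neither case.

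**Working it through.** **Inputs.** From Sample size and analysis: 800 women, difference 0.3 g/dL, SD at most 1.3 g/dL, two-sided 0.05. From Preliminary Data: 53 women, mean fall 1.02 g/dL, 95% CI 0.74 to 1.29. Equal arms are assumed; the odd/even rule under Randomization gives 1:1 in expectation. Loss rates of 10%, 20% and 30% are assumptions, as the documents give none.

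**1. The plan's figure reproduces.** For a two-sample t-test with n per arm, the noncentrality is 0.3 / (SD × √(2/n)). With n = 400 and SD 1.3 this is 0.3 / (1.3 × √0.005) = 3.26. The noncentral t with 798 df gives power 90.3%. The smallest equal-arm total reaching 90% is 792 (790 gives 89.96%). The room for loss is therefore 8 of 800, or 1%.

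**2. The SD of the change, from the pilot.** Half-width = (1.29 − 0.74)/2 = 0.275. SD = 0.275 × √53 / t(0.975, 52) = 0.275 × 7.280 / 2.007 = 0.998. The 95% limits are 0.998 × √(52/73.81) = 0.84 and 0.998 × √(52/33.97) = 1.23. For 90% power, 468 must be analysed at 0.998 and 714 at the upper limit. Tolerable losses are 1 − 468/800 = 41% and 1 − 714/800 = 11%. Rounding of the pilot interval moves the latter to between about 7% and 14%.

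**3. Power for 0.3 g/dL by number analysed** (same formula):

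| Analysed (assumed loss) | SD 1.3 | SD 1.00 | SD 1.23 |
|---|---|---|---|
| 800 (0%) | 90.3% | 98.9% | 93.0% |
| 720 (10%) | 87.1% | 98.1% | 90.3% |
| 640 (20%) | 83.0% | 96.7% | 86.6% |
| 560 (30%) | 77.8% | 94.4% | 81.9% |

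The SD 1.3 column applies to a comparison of concentrations; the other two apply to a comparison of change. At SD 1.3 the difference detectable with 90% power becomes 0.315, 0.334 and 0.357 g/dL at 720, 640 and 560.

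**4. What the paired test would show.** Within one arm, expected t = fall / (SD of change / √n).

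- Pilot: 1.02 / (0.998/√53) = 7.4.
- 320 per arm (assumes 20% loss), fall 1.02: 1.02 / (0.998/√320) = 18.3.
- 320 per arm, fall smaller by the full 0.3, that is 0.72: 0.72 / (0.998/√320) = 12.9.
- At the upper-limit SD of 1.23 the last two become 14.8 and 10.4.

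All of these correspond to P<0.0001. Significance in both arms would be expected with or without a misoprostol effect.

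**The case against.** The strongest reply is that a between-arm test is plainly meant. Study Design compares two groups, the power statement speaks of a treatment difference, and the 90% comes out only if a two-sample test was used. The documents also do not say that the paired test is to be run separately by arm. The intent is fair to infer, and it stands. But the test and the endpoint are still not stated, and the one test that is stated cannot supply the comparison.

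A second reply is that the loss of power has limited consequence. On the stated SD, a 10% loss moves the detectable difference only from 0.30 to about 0.31 g/dL. The 1.3 is a ceiling, and all loss rates here are assumed. This also stands, and it is why power is the secondary part of the point. A reader might infer from the SD 1.3 column that the trial is too small. The documents do not support that: the site's own change data suggest 90% could survive substantial loss. Nor do they guarantee adequacy, because at the upper limit of the pilot SD the margin is only about 11%.

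On episiotomy, the Study Procedure wording may be no more than shorthand for the fuller list, and the unclear parenthesis does not prevent a forecast. It means only that a forecast is needed under each reading.

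**Conclusion.** The point holds as an analysis-specification fault, with a power statement attached to the wrong number. The named paired t-test does not compare the arms, and run by arm it would be significant in both regardless of treatment effect. The plan's arithmetic is right for a two-sample comparison with 800 analysed at SD 1.3. On that basis it fails once more than 1% of entrants are not analysed, giving 87%, 83% and 78% at assumed losses of 10%, 20% and 30%.

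An underpowered trial is not shown. On the change score, 468 analysed suffice at the pilot SD, or 714 at its upper limit. That relief assumes the pilot SD carries over. The pilot was 53 spontaneous vaginal deliveries, with no statement that the trial's eligibility rules or later exclusions were applied. The point does not concern bias from excluding women after randomization, and correcting it would not remove that bias. It should be corrected.

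**What to change.** In Sample size and analysis:

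1. Name the treatment comparison. Either use the between-arm difference in postpartum hemoglobin adjusted for admission hemoglobin (both are already collected, under Results – includes Follow-up Data), or a two-sample comparison of change. The paired t-test may stay as a description of the fall, not as the test of treatment.
2. State the SD of the quantity analysed. For the change score, 1.00 g/dL is the pilot point estimate and 1.23 the cautious case. For the adjusted analysis, 1.00 is likely conservative. Note that the pilot states no use of the trial's exclusions.
3. State entered and analysed numbers separately, with an assumed exclusion share, which site delivery records could inform. Restate power for 0.3 g/dL at the analysed number, at both the point estimate and the upper limit of the SD. If SD 1.3 is kept, replace 90% with the power at the analysed number.
4. Reconcile Inclusion and exclusion criteria with Study Procedure on the scope of the episiotomy exclusion. Until then, give the analysed number under both readings.

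**Cost.** A change to the named analysis, a short look at delivery records, and one wording reconciliation, with no new patient data. The stated power becomes less favourable on the SD 1.3 basis. No enrolment is added, because the fix restates power and does not defend 90% at SD 1.3. Defending it would take 792/0.9 = 880, 792/0.8 = 990 or 792/0.7 = 1,132 entrants at 10%, 20% or 30% loss, and the pilot data do not show that this is needed.

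### The only test named is a within-woman paired t-test, so the plan specifies no analysis that compares oxytocin plus misoprostol with oxytocin alone

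*Combined protocol and SAP*

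**What the plan says.** The Abstract gives the objective as finding out whether adding misoprostol alters blood loss. The Study Design section sets up a contrast of hemoglobin and hematocrit "in a group of parturients who received standard prophylactic intravenous oxytocin immediately after delivery with a group that received oxytocin and adjuvant misoprostol".

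The section Sample size and analysis calls the trial a two-treatment parallel design. It claims 90% power at a two-sided 0.05 level "if the difference in hemoglobin concentration between treatments is 0.3 g/dL", assuming that "the standard deviation of the postpartum and intrapartum hemoglobin concentrations is not larger than 1.3 g/dL".

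The analysis itself takes two sentences in the same section: "Comparison of intrapartum and postpartum hemoglobin and hematocrit levels will be done using a paired t-test", and "A probability level of 0.05 will be used as the threshold for significance". No other section names a test, a model or an effect estimate.

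**The concern.** A paired t-test needs two measurements on the same unit, or matched units. Here the pairs are the intrapartum and postpartum values of one woman, and the null hypothesis is that the mean fall is zero. The two arms contain different, unmatched women, so this test cannot compare them.

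Whether hemoglobin falls after delivery is already settled by the protocol's own pilot of 53 women, reported in Preliminary Data: "The mean fall was 1.02 (95% CI 0.74, 1.29), a statistically significant decrease (P<0.0001". Repeating the test with several hundred women per arm will give a significant result in both arms whatever misoprostol does. Setting one arm's p-value beside the other's is not a valid substitute, since both are expected to be extreme in either case.

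With no between-arm test specified, the real efficacy analysis would be chosen after the data are in. The options include postpartum level, absolute change, percentage change or baseline-adjusted level, for hemoglobin or hematocrit. The trial is open-label and removes some randomized women from the analysis post hoc, so that freedom is a genuine route to bias.

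**Working it through.** **Inputs.** From Sample size and analysis: total 800, difference 0.3 g/dL, SD 1.3 g/dL, two-sided alpha 0.05, power 90%. From Preliminary Data: n = 53, mean fall 1.02 g/dL (95% CI 0.74 to 1.29), SD 1.2 g/dL on admission and 1.3 g/dL postpartum. Assumption: 400 per arm. The protocol states no ratio, but the odd/even rule under Randomization implies roughly 1:1.

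**1. Reproducing the sample size.** For two independent means:

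n per arm = 2 × SD² × (1.960 + 1.282)² / difference² = 2 × 1.69 × 10.51 / 0.09 ≈ 395, or 790 in total.

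Power at 400 per arm is 0.903 (noncentral t). The stated 800 and 90% are therefore reproduced by a comparison of two independent groups. A paired test of a 0.3 g/dL change with SD 1.3 would need only about 198 women. The sizing thus presupposes a test that the analysis text does not name.

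**2. SD of the within-woman change.**
- CI half-width = (1.29 − 0.74)/2 = 0.275.
- SE = 0.275 / 2.007 = 0.137, using t(0.975, 52 df).
- SD of change = 0.137 × √53 ≈ 0.998 g/dL.

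**3. Behavior of the stated test in an arm of 400.** t = mean fall / (SD of change / √400).

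| SD of change (g/dL) | Fall 1.02 (no benefit) | Fall 0.72 (1.02 − 0.3) |
|---|---|---|
| 0.998 (pilot) | t = 20.4, p ≈ 4e-64 | t = 14.4, p ≈ 3e-38 |
| 1.3 | t = 15.7 | t = 11.1 |
| 1.84 (1.3 × √2: SD 1.3 at both times, zero correlation) | t = 11.1 | t = 7.8, p ≈ 4e-14 |

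Even at the pessimistic SD in the last row, the test rejects in both columns.

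**4. Simulation.** 5,000 trials, 400 per arm, normally distributed changes. The paired columns apply to each arm separately and to the arms pooled.

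| SD of change (g/dL) | Paired test, no effect | Paired test, 0.3 benefit | Two-sample test of change, no effect | Two-sample test of change, 0.3 benefit |
|---|---|---|---|---|
| 0.998 | 100% | 100% | 5.1% | 98.8% |
| 1.3 | 100% | 100% | 5.1% | 90.8% |

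**5. What a between-arm analysis would deliver at 400 per arm for 0.3 g/dL.**
- Pilot-implied correlation = (1.2² + 1.3² − 0.998²) / (2 × 1.2 × 1.3) = 0.684.
- ANCOVA residual SD = 1.3 × √(1 − 0.684²) = 0.948 g/dL.

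| Analysis | SD (g/dL) | Power |
|---|---|---|
| Postpartum level, unadjusted | 1.3 | 0.903 |
| Two-sample t-test of change, pilot SD | 0.998 | 0.989 |
| Two-sample t-test of change, zero correlation | 1.84 | 0.635 |
| ANCOVA, pilot correlation | 0.948 | 0.994 |

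The correlation comes from 53 women. An approximate 95% interval (Fisher z) is 0.51 to 0.81, giving a residual SD of 0.77 to 1.12. At 1.12, ANCOVA power is still about 0.97. With zero correlation the ANCOVA residual SD returns to 1.3, so its power is essentially that of the unadjusted comparison.

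**The case against.** The strongest reply is that the between-arm aim is plain. The Abstract, the Study Design section and the power statement all describe it, and the power statement even fixes alpha and sidedness: "the probability is 90% that the study will detect a treatment difference at a two-sided 0.05 significance level". The sample size reproduces as a two-group calculation, so the authors evidently had such a test in mind. On a charitable reading, the paired sentence describes only how each woman's fall is obtained, with the arms contrasted afterwards.

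The aim is indeed present, and this point does not say otherwise. But the protocol nowhere states the charitable reading, and a two-sample test of paired changes is a different procedure from a paired t-test. An analyst who followed the text literally would produce no treatment comparison.

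Two narrower points stand:
- ANCOVA is not the only acceptable repair. With the pilot SD, a two-sample t-test of the change has almost the same power (0.989 against 0.994). Leaving admission hemoglobin out as a covariate is a loss of efficiency, not an error.
- The pilot correlation is imprecise, so the ANCOVA gain is approximate.

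Neither point rescues the stated test.

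**Conclusion.** The concern holds, and the plan is wrong as written. The single test specified addresses a question that is not the trial's. It is expected to be significant in both arms whether misoprostol has no effect or the full 0.3 g/dL effect: t is about 20 and 14 with the pilot SD of change, and still about 11 and 8 at an SD of 1.84 g/dL. The analysis text also contradicts the objective and the sample-size calculation beside it.

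These figures rest on three assumptions: 400 women per arm, a mean fall on oxytocin close to the pilot's 1.02 g/dL, and an SD of change no larger than 1.84 g/dL. The basic point, that a within-woman test does not contrast the arms, needs none of them. This must be fixed before the analysis is done.

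**What to change.** Replace the paired t-test sentence with, for example:

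*Primary analysis: ANCOVA of postpartum day 1 hemoglobin on randomized group, adjusted for admission hemoglobin, two-sided alpha 0.05, reporting the adjusted between-group difference with its 95% CI. The same model for hematocrit is secondary. Within-group paired changes are descriptive only.*

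If the sponsor prefers a two-sample t-test of the change in hemoglobin, that also closes the gap, provided it is named as primary in advance. ANCOVA is the safer choice because its power does not depend on a high correlation between the two measurements: in the zero-correlation case it keeps about 90%, while the change-score test drops to about 64%.

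The cost is one paragraph of protocol text. Admission and postpartum day 1 hemoglobin and hematocrit are already on the Data Collection list, so no extra data are needed. Setting aside losses to the post hoc exclusions, for which the protocol gives no rate, 800 women are enough for the ANCOVA if the postpartum SD is no larger than 1.3 g/dL.
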